In a national survey of 129 neonatal nurses from 35 states, we found that while over 98% stated oral care was important for the health of VLBW infants, less than 37% felt their NICU adequately addressed oral care. In addition, tremendous variation existed in practices regarding oral care including the method, timing, equipment and whether or not oral care was even performed.

5. Specific Aims:

The long-term goal of this research is to improve short and long-term health outcomes for premature very low birth weight (VLBW; <1500 grams) infants by decreasing complications caused by lack of frequent standardized oral care.

Specific aims are as follows:

Aim 1: To compare the oral microbiome between groups including bacterial pathogenicity determinants.

Aim 2: To compare respiratory outcomes including the incidence of ventilator associated pneumonia, bronchopulmonary dysplasia and need for respiratory support between groups.

6. Research Plan:

Sample and Setting:

The proposed study will prospectively follow 217 VLBW infants and 217 mothers (dyad) for 4 weeks following birth (includes 69 previously enrolled mother/infant dyads). Infants will be randomized into 1 of 3 groups. Standardized oral care will be performed every 3-4 hours (Group 1) and every 12 hours (Group 2) using sterile water. Group 3 will have standardized oral care performed every 3-4 hours using human milk (mother's breast milk or donor breast milk). Mothers of multiples will also be potential subjects. UF NICU nursing staff will receive UF Qualtrics survey links to their UF email yearly. Survey responses are voluntary and anonymous and will include up to 225 RN responses.

Infants will be sampled by convenience from the NICU at UF Health Shands Children's Hospital. Approximately 150 premature VLBW infants are admitted to this NICU per year. Our consent rate in similar studies is > 60% which strongly suggests we will be able to recruit 217 infants and 217 mothers (dyad) over a 12-month period.

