The proposed randomized controlled pilot study will follow a prospective cohort (n=217) of racially and economically diverse premature VLBW male and female infants following birth. Infants will be randomly assigned to one of three groups using a randomized blocks approach as implemented in SAS PROC PLAN. A randomized blocks approach will ensure comparable treatment group sizes, and a priori assignment will reduce possibility of bias in treatment group assignment. All groups will receive standardized oral care for 4 weeks. Infants in Group 1 will have standardized oral care performed every 3-4 hours with sterile water (dependent on scheduled care times), infants in Group 2 will have standardized oral care performed every 12 hours with sterile water, and Group 3 will have standardized oral care performed every 3-4 hours (dependent on scheduled care times) with human milk. Groups were chosen based upon recommendations for adults (every 3-4 hours) and data regarding common practices of neonatal nurses obtained from our national survey (every 12 hours) and the benefits of placing drops of human milk into the oral cavity of preterm infants.

Inclusion criteria: 1) mothers who are ≥ 18 years of age, 2) infant (s), including multiples, born at ≤ 30 weeks, 3) infant with birth weight at ≤ 1500 grams

Exclusion criteria: 1) infants with born congenital anomalies of the face, lungs, or gastrointestinal system 2) infant not expected to live > 7 days following delivery

Informed consent will be will be obtained from the mother or father within 72 hours after birth at the infant's bedside or in the mother's hospital room.

Procedure:

Oral care will be performed in infants in Group 1 (every 3-4 hours) using sterile water, Group 2 (every 12 hours) using sterile water and Group 3 (every 3-4 hours) using human milk (if mother's breast milk, not available, donor breast milk will be used). The following procedure and a checklist to ensure treatment fidelity. Equipment will be easily accessible and provided in sterile pre-packaged kits at the infant's bedside. Study personnel involved with subjects will be unable to be blinded since information regarding oral care is visually obvious and recorded in the chart by nursing staff. However, those performing analysis of saliva and collecting data on respiratory outcomes will be blinded to the infant's designated group. Feeding tubes will be changed no less than every 7 days.

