To determine bacteria in the infant's mouth which may originate from the mother's breast milk or donor milk, a small sample of breast milk (3-5 mL) will be obtained from the infant's mother (after her consent) at the end of week 1 and 4 and 16S rRNA sequencing will be performed. Samples will be obtained from the NICU milk room. If mother is pumping < 5mL/, no sample will be obtained but no deviation reported. If donor breast milk is used for oral care (mother is not providing breast milk to her infant), 3-5 mL of donor breast milk will be obtained and 16s rRNA sequencing performed

Aim 2: will compare respiratory outcomes including evidence of VAP (positive ETT culture, incidence of ventilator associated events), days on invasive and non-invasive respiratory support, and incidence of BPD between groups. We hypothesize that infants who undergo standardized oral care every 3-4 hours will have less VAP, require fewer days of respiratory support, and have less BPD than Group 2. Descriptive statistics, including confidence intervals, will be generated to describe the distribution of days of respiratory support in each group, and measures of effect size (Cohen's *f*) will be calculated from the between-subjects (Treatment Group, with 3 levels) general linear model (GLM). Incidence of occurrence for VAP and BPD will be described for each group using frequencies and percentages along with confidence intervals for the proportions. Effect sizes (Cohen's *w*) for each of those two outcome variables will be calculated from a 3 (Treatment) by 2 (Occurrence) contingency table.¹⁹

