A yearly anonymous and voluntary survey will be administered to the NICU nursing staff using a UF Qualtrics link sent to their email regarding staff concerns and questions. An IRB approved waiver of consent, will be sent with each survey, with an expected response of 225 staff. Yearly Q & A sessions will be scheduled as needed for staff questions and/or concerns. To encourage protocol compliance, nurses will receive quarterly emails or flyers will be posted with study updates or information important to study compliance. New nurses will be

formally oriented to the study during their orientation period. We have previously successfully used these strategies.

Data Entry and Management

All data will be entered into REDCap by a research assistant and verified by a Research Coordinator. A unique identifier will be assigned to each enrolled participant that will serve as the unique subject ID. Personal Health Information will not be stored in the study database. The study case report forms (CRFs) will be maintained in study specific folders. The CRFs are considered the primary data collection instruments for this study. When CRFs are not actively being processed, they will be secured in locked file cabinets. In addition to the use of passwords and other security measures, all documents containing identifying information are considered confidential materials and are safeguarded to the greatest possible extent. No individually identifying information will be released or discussed with anyone other than study staff.

Table 1. Instruments

Variable	Measurement	Timing
Descriptive (1-2) below		
1. Maternal, prenatal and perinatal demographics	Data extracted from medical record: Maternal history, prenatal and perinatal complications and medications, mode of delivery, whether mother received antibiotics and/or antenatal steroids	Collected upon entry into study.
2. Infant demographics	Data extracted from medical record: Race/ethnicity, sex, gestational age, birth weight, Apgar scores, resuscitation at birth and neonatal acuity (SNAP II) score	Collected upon entry into study.
3. Infant data	Type and amount of feeding, whether or not the infant is NPO, number of days and type of antibiotics, whether the infant was diagnosed with oral thrush and type of treatment. Length of skin-to-skin care	Collect upon entry into study and until infant discharge
Respiratory Factors (1-2)		

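### The stated Aim 2 analyses make no use of gestational age or birth weight, both collected at entry, and so give up precision that adjustment would recover at almost no cost

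*Protocol*

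**What the plan says.** **Allocation.** Section 6 of the protocol (Sample and Setting) states "Infants will be randomized into 1 of 3 groups", done "using a randomized blocks approach as implemented in SAS PROC PLAN". The benefit claimed for blocking is size: "A randomized blocks approach will ensure comparable treatment group sizes". No stratification factor is named.

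**Aim 2 analyses.** For days of respiratory support, the effect size (Cohen's *f*) is "calculated from the between-subjects (Treatment Group, with 3 levels) general linear model (GLM". For VAP and BPD, the effect size (Cohen's *w*) is "calculated from a 3 (Treatment) by 2 (Occurrence) contingency table", with percentages and confidence intervals by group. No covariate is named for any of the three outcomes.

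**Baseline data.** Table 1 lists, as infant demographics extracted at study entry, "Race/ethnicity, sex, gestational age, birth weight, Apgar scores, resuscitation at birth and neonatal acuity (SNAP II) score". The block of Table 1 that is labelled as covariates contains only the analysis of maternal and donor milk.

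**Size.** The study "will prospectively follow 217 VLBW infants and 217 mothers (dyad) for 4 weeks following birth", a number that includes 69 dyads already enrolled.

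**The concern.** Days of support and an oxygen requirement at 28 days can be expected to depend on how immature the infant is at birth. The protocol's Background itself names physiologic immaturity as a source of morbidity risk. Eligibility sets an upper limit on gestational age and on birth weight but no lower limit on either.

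If maturity explains part of the outcome and is left out, that part stays in the error term. Confidence intervals are then wider than the data require, and the estimated group differences carry whatever difference in maturity chance has produced. Blocking for group size does nothing about this. The aim's deliverables are intervals and effect sizes, which are the quantities that unexplained variation degrades.

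The protocol does not simply leave the analysis open. It names the model and its factor, and it names the table. The variables needed to improve on them are already on the data collection list.

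**Working it through.** **Inputs from the protocol:** 217 infants and three groups. Equal allocation is my assumption, since the text promises only comparable sizes; 217 / 3 ≈ 72 per arm.

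**Inputs not in the protocol:** the share of variance in support days explained by entry covariates (R²), taken here as 0.1, 0.3 and 0.5. For Aim 2 the protocol states no significance level, power, standard deviation or effect size. Where a test is needed for illustration I use two-sided 5%. There is no stated figure to reproduce.

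**Step 1: precision.** Adjustment multiplies the residual SD, and so the standard error, by √(1 − R²). The unadjusted trial with the same precision needs 217 / (1 − R²) infants.

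| Assumed R² | SE factor | SE reduction | Equivalent unadjusted N |
|---|---|---|---|
| 0.1 | √0.9 = 0.949 | 5% | 217/0.9 = 241 |
| 0.3 | √0.7 = 0.837 | 16% | 217/0.7 = 310 |
| 0.5 | √0.5 = 0.707 | 29% | 217/0.5 = 434 |

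**Step 2: the same gain as power (illustration only).** The pairwise difference detectable with 80% power at 72 per arm is (1.960 + 0.842) × √(2/72) = 0.467 SD. With adjustment, power for that difference becomes 84%, 92% and 98% for R² of 0.1, 0.3 and 0.5.

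**Step 3: chance imbalance.** The standardised difference in a baseline variable between two arms has SD √(2/72) = 0.1667. A difference above 0.25 SD is 0.25 / 0.1667 = 1.5 standard errors, so its probability for a given pair is 2 × P(Z > 1.5) = 13%. Simulating three arm means (400,000 draws) gives 29% that at least one of the three pairs exceeds 0.25 SD.

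**Step 4: effect of such an imbalance.** Given a 0.25 SD difference in maturity, the unadjusted contrast moves by 0.25 × √R² outcome SDs. Divided by 0.1667, this gives the shift in standard errors, μ. Conditional on that imbalance, the unadjusted test statistic has mean μ and SD √(1 − R²) when there is no treatment effect. The probability that it falls beyond ±1.96 follows.

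| Assumed R² | Shift (SD) | μ (SE units) | Conditional type I error |
|---|---|---|---|
| 0.1 | 0.08 | 0.47 | 6.4% |
| 0.3 | 0.14 | 0.82 | 8.7% |
| 0.5 | 0.18 | 1.06 | 10.2% |

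These error rates are conditional on the imbalance. Averaged over all allocations the rate is 5%.

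**Step 5: room for covariates in VAP.** The protocol gives no VAP rate, and VAP as defined arises only in ventilated infants. If 10% of all infants had it (my assumption), there would be 0.10 × 217 ≈ 22 events. Two treatment terms plus one covariate leave about 22/3 ≈ 7 events per slope; two treatment terms plus three covariates leave 22/5 ≈ 4.

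**The case against.** The strongest reply has four parts.

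*Covariates belong in the analysis plan.* That plan is not at hand, and the protocol neither calls the model unadjusted nor rules covariates out. This stands as a caution: one cannot infer that adjustment is forbidden. But the protocol does state the model with one factor and the binary analyses as a two-way table, so a plan that adjusted would go beyond what is written here.

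*The stated analysis is valid.* This stands in full. A reader might infer from the imbalance figures that the comparison is biased, or that an imbalance in maturity would be mistaken for a treatment effect. The documents do not support that. Treatment is randomised, the unadjusted estimate is unbiased over randomisation, and its interval already allows for chance imbalance.

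*The study calls itself a pilot and Aim 2 is largely descriptive.* This lowers the stakes but does not remove the point, because interval width is what a descriptive aim reports. It does follow that a smaller unadjusted Cohen's *f* is not an error: unadjusted and adjusted *f* use different denominators, and both are legitimate.

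*The size rests on an assumed R².* This stands. At R² = 0.1 the gain is only 5%. The 0.25 SD cut is a convention, and 29% refers to any of three pairs. The √(1 − R²) argument covers support days only; no gain has been quantified for BPD or VAP.

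**Conclusion.** The point holds as a worthwhile, low-cost improvement to a stated analysis. It does not show bias or an invalid test. For support days, the standard error could fall by about 5-29% for an assumed R² of 0.1-0.5, worth between 24 (241 − 217) and 217 (434 − 217) additional unadjusted infants. The chance of a maturity difference above 0.25 SD is about 13% for a given pair and 29% for some pair, with 72 per arm and equal allocation assumed. For BPD and VAP the direction of the argument is the same, but its size is not established.

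A reader might go further and ask that the randomisation list be rebuilt within maturity strata. The documents do not make that necessary. Blocking without stratification is a legitimate choice and meets its stated purpose. A new list could not reach the 69 dyads already enrolled, and although 217 − 69 = 148 remained when this version was written, current enrolment is unknown. Covariate adjustment covers all 217 infants without touching the list.

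**What to change.** 1. **Support days:** prespecify gestational age and/or birth weight as covariates in the general linear model, and report adjusted group differences with confidence intervals.
2. **BPD:** add a logistic model with treatment group and the same maturity covariate or covariates, reported as adjusted risk differences.
3. **VAP:** because events may be few, use at most one maturity covariate or a penalised logistic model.
4. **Keep** the planned unadjusted summaries, Cohen's *f* and Cohen's *w* alongside.

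The choice of covariates should be fixed before outcomes are examined by group. No new data and no change to the randomisation list are needed. The cost is a few degrees of freedom and a little more analysis work.

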1. Using a sponge-tipped swab saturated with sterile water or human milk, the bedside nurse or research coordinator (with extensive NICU nursing experience) will clean all 4 quadrants of the gum surfaces and upper posterior part of the oropharynx for 15 seconds each.
2. Using a new sterile water or human milk saturated swab, they will clean the ventral and posterior surfaces of the tongue for 15 seconds.
3. Using a new sterile water or human milk saturated swab, they will gently clean the outer surface of the endotracheal tube (if present), feeding tube or other oral tubes.
4. The lips will be cleaned with a sterile gauze saturated with sterile water or human milk.
5. The oral cavity will be suctioned as needed with an oral suction device to remove secretions (oral suction devices are changed every 24 hours per NICU protocol).
6. After the above oral care is complete, 0.1 mL of mom's breast milk will be placed into each buccal cavity (if available) until reaching day of life #7, if infant meets the NICU policy of a birth weight of \leq 1250 grams. Orally administered breast milk is routine nursing care for premature infants in this NICU and may interact with the oral lymphoid tissue to help support immune system development.¹⁵

Aim 1 will determine the effect of standardized frequent oral care using human milk on the oral microbiome including bacterial pathogenicity determinants in premature VLBW infants. We hypothesize that standardized oral care performed every 3-4 hours using human milk will be associated with less dysbiosis than standardized oral care every 3-4 hours or 12 hours using sterile water. A sample of the infant's saliva will be collected weekly for 4 weeks by the research coordinator (a registered nurse experienced in the care of critically ill infants) by gently inserting a sterile brush into the infant's mouth and gently rotating the swab. Collection will occur immediately prior to the infant's scheduled oral care. Our team is skilled in the collection, processing and analysis of infant saliva.

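### Step 6 gives mother's milk to eligible infants in every group with no stated schedule; if it follows each session, Group 1 vs Group 2 does not isolate cleaning frequency in infants of 1250 g or less

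*Protocol*

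**What the plan says.** Protocol section 6 (Sample and Setting) describes Groups 1 and 2 as receiving oral care with sterile water and Group 3 with human milk. Groups 1 and 3 are treated every 3-4 hours; for the third, "infants in Group 2 will have standardized oral care performed every 12 hours with sterile water". Care lasts 4 weeks.

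The Procedure is one list for all groups. Steps 1-4 let the liquid vary by group. Step 6 does not: "After the above oral care is complete", 0.1 mL of mother's "breast milk will be placed into each buccal cavity (if available) until reaching day of life #7". The step applies "if infant meets the NICU policy of a birth weight of" 1250 g or less. Trial entry is at 1500 g or less, so the cut-off falls inside the trial population. The next sentence reads "Orally administered breast milk is routine nursing care for premature infants in this NICU" and adds that the milk might act on immune tissue in the mouth.

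The Aim 2 hypothesis sets care every 3-4 hours against Group 2. Its general linear model (GLM) for days of respiratory support has treatment group, with three levels, as the only named term. Table 1 lists birth weight at entry and, in the enteral intake row, a count of colostrum buccal swabs. The milk entry under Covariates concerns the sequencing of the milk, not how often it was placed in the mouth.

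**The concern.** Group 1 vs Group 2 is the only pair that differs in frequency without a planned difference in milk. Group 3 differs from Group 2 in both respects by design. A reader who wants to know what more frequent cleaning does must therefore rely on Group 1 vs 2.

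Step 6 has no times per day of its own. If it is carried out whenever oral care is completed, the number of milk placements rises with the randomised frequency, and this pair also differs in milk exposure among eligible infants. The protocol does not treat oral milk as inert: besides the immune remark in step 6, the choice of groups rests partly on "the benefits of placing drops of human milk into the oral cavity of preterm infants". A difference between Groups 1 and 2 could then not be credited to cleaning frequency alone.

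**Working it through.** The protocol gives no figure for step 6 exposure, so there is none to reproduce. The check derives exposure under each reading.

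**Inputs (Protocol section 6).** Intervals: 3-4 h (Groups 1 and 3), 12 h (Group 2). Volume: 0.1 mL in each of two cheeks = 0.2 mL per placement. Consent within 72 hours of birth. Step 6 ends on reaching day of life 7. Study care lasts 28 days.

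**Window under study care.** At most 7 days, if study care starts at birth. With consent at 72 hours it is 3 or 4 days, depending on how days of life are counted, which is not defined. As a share of 28 days: 3/28 = 10.7%, 4/28 = 14.3%, 7/28 = 25.0%.

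**Reading A: one placement per session.** Placements per day = 24 / interval: 24/3 = 8 and 24/4 = 6 in Group 1; 24/12 = 2 in Group 2. Ratio 6/2 = 3 to 8/2 = 4.

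| Window | Group 1 placements | Group 1 volume | Group 2 placements | Group 2 volume |
|---|---|---|---|---|
| 3 days | 18-24 | 3.6-4.8 mL | 6 | 1.2 mL |
| 4 days | 24-32 | 4.8-6.4 mL | 8 | 1.6 mL |
| 7 days | 42-56 | 8.4-11.2 mL | 14 | 2.8 mL |

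The ratio does not depend on the window.

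**Reading B: a NICU schedule common to all groups.** Placements are the same in Groups 1 and 2, so the ratio is 1.

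**Scale against Group 3.** Group 3 has 6 x 28 = 168 to 8 x 28 = 224 oral-care sessions with milk. By count, step 6 in an eligible Group 1 infant under Reading A is 18/168 = 10.7% to 56/224 = 25.0% of that. Pooling Groups 1 and 3 against Group 2 therefore brings in far more milk than step 6 does.

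**Scale across a whole arm.** The share of infants who are 1250 g or less with mother's milk available is not given. Assuming a share p, step 6 covers p x (10.7% to 25.0%) of an arm's treatment days: 2.7-6.2% for p = 0.25, 5.4-12.5% for 0.50, 8.0-18.8% for 0.75 and 10.7-25.0% for 1.00.

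**Birth weight in the GLM.** If birth weight explains a share R² of the variance in days of respiratory support, standard errors shrink by the factor sqrt(1 - R²). For R² = 0.10, 0.20 and 0.30 (assumed) this is 0.949, 0.894 and 0.837, a reduction of about 5% to 16%.

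**The case against.** The strongest reply is that there is no contradiction. Sterile water names the cleaning liquid in steps 1-4; step 6 is a separate act afterwards, and its opening words may fix the order within a session rather than how often the step is done. The step takes its weight limit from a NICU policy and calls the practice routine, so the frequency may well be set by a schedule that ignores the randomised group. This stands: the per-session reading is literal and natural but not established, and the defect is an unstated schedule.

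The reply can add that Aim 2 never claims a pure frequency contrast. Its hypothesis covers Groups 1 and 3 together, the study is called a pilot, and the Aim 2 analysis consists of confidence intervals and effect sizes. This also stands, and it limits the weight of the point. It does not remove it, because conclusions about frequency are what a reader will want from Group 1 vs 2.

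Two further objections hold. The swab item in Table 1 is worded for colostrum and may not count step 6 placements. And birth weight cannot simply be added to the 3 x 2 tables for VAP and BPD or to the planned microbiome tests; the covariate list could also be extended in an analysis plan not seen here.

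A reader might infer that step 6 biases the trial or breaks the randomisation. The documents do not support that: "Infants will be randomly assigned to one of three groups using a randomized blocks approach", and whatever milk follows from the assigned care belongs to the package being compared.

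**Conclusion.** The point holds as a gap in the procedure with a conditional consequence. On the per-session reading, infants of 1250 g or less with mother's milk available receive 3-4 times as many placements in Group 1 as in Group 2, for roughly 11-25% of the treatment period. On the common-schedule reading, Groups 1 and 2 do not differ in milk, and what remains is a slight early dilution of Group 3 vs Group 1.

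It would go too far to say that Group 1 vs 2 is known to be confounded, or that the sterile-water label is false. Neither follows from the text. The size and direction of any effect on VAP, BPD, days of support or the microbiome cannot be derived, because the protocol gives neither the eligible share nor an effect of buccal milk. The point merits correction because the remedy is cheap and an analysis plan cannot establish afterwards what bedside staff were told. Confidence is medium, since the NICU policy itself is not at hand.

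**What to change.** 1. Reconcile step 6 with the group descriptions: state whether it applies in all groups and whether it follows the randomised sessions or a common schedule. Which is right is a clinical matter on which nothing is proposed here. The planned sample "includes 69 previously enrolled mother/infant dyads"; document what was done for them.

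2. Have the sponsor confirm whether the colostrum buccal swab count in Table 1 captures step 6 placements. If so, tabulate it by group in infants of 1250 g or less up to day of life 7. Do not adjust for it, because it arises after randomisation. State in advance that if the count tracks the randomised frequency, Group 1 vs 2 is not a pure frequency effect.

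3. Separately, and for precision only, add birth weight to the GLM for days of respiratory support. Leave the 3 x 2 tables and the microbiome tests as planned.

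**Cost.** A wording change, one table, and one covariate known at birth that uses one degree of freedom; randomisation is unchanged. For 69 of 217 dyads (69/217 = 31.8%) the new text can only describe past practice. If the swab item does not capture step 6, the table cannot be made from it and the limit must rest on documented practice.

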DNA Extraction & 16S rRNA sequencing. DNA will be extracted from saliva using PowerFecal DNA isolation kit (MO BIO Laboratories) and quantified using a Nanodrop spectrophotometer (Thermo Scientific, Wilmington, DE). V4 universal primers will be used for 16S rRNA amplification and subsequent Illumina MiSeq sequencing. Samples will be amplified in 25 μ l reactions containing 0.5 Units Phusion High-Fidelity Polymerase (New England Biolabs, Ipswich, MA), 1X Phusion HF Reaction Buffer, 0.75 μ l DMSO, and 0.2 mM each dNTP. Triplicate PCR amplifications will be pooled for each sample, and cleaned with a QIAquick PCR Purification kit (Qiagen). 200 nanograms of each cleaned amplicon library will be submitted for sequencing at the ICBR core facility at UF. Sequencing will be performed on an Illumina MiSeq with a 300-bp paired-end protocol, using single indexing.

Microbiome 16S rRNA Gene Analysis. Sequencing reads will be parsed by Illumina index at the sequencing center. Paired reads will be merged, and primers and adaptors will be removed using a combination of tools in cutadapt, Galaxy, and eutils. Sample names will be added to the definition lines of sequencing reads using sed and concatenated into one fasta file, to make them compatible for analysis in QIIME v1.9.¹⁶ Clustering of Operational Taxonomic Units (OTUs) at 97% similarity will be performed with the subsampled open-reference OTU picking method,¹⁷ with no removal of singletons. The Greengenes reference dataset version 13.8 will be used as the reference for OTU picking and for taxonomy assignment with uclust.¹⁸ Community structure will be analyzed in R with phyloseq and will be plotted with ggplot2. Analysis of similarities (ANOSIM) will be performed in R using VEGAN v2.0-8. Statistical significance of QIIME profiles will be assessed using STAMP for comparison of two independent groups. TIME will be utilized for analysis of the longitudinal microbiome data. These tests are appropriate for analysis between groups and over time.

Stool samples will be collected at the end of week 1 and 4 by the research nurse. Following collection, all samples will be placed in a sterile specimen container and immediately frozen at -80 degrees Celsius for later analysis for inflammatory markers and 16S rRNA sequencing.

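### Keeping every singleton adds nothing to the comparison between groups, and 97% OTUs are coarser than the milk-origin question needs; both can be improved on the same reads

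*Protocol*

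**What the plan says.** Protocol section 6, under DNA Extraction & 16S rRNA sequencing, limits the assay to one region: "V4 universal primers will be used for 16S rRNA amplification and subsequent Illumina MiSeq sequencing". The next paragraph, Microbiome 16S rRNA Gene Analysis, fixes the processing: "Clustering of Operational Taxonomic Units (OTUs) at 97% similarity will be performed", by open-reference picking, "with no removal of singletons". The reference is also fixed: "The Greengenes reference dataset version 13.8 will be used as the reference for OTU picking and for taxonomy assignment with uclust". Between merging the reads and clustering them, only primer and adaptor removal is described. No chimera step, abundance filter or prevalence filter is named.

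Two of the analyses that follow are "Analysis of similarities (ANOSIM) will be performed in R using VEGAN v2.0-8" and "Statistical significance of QIIME profiles will be assessed using STAMP for comparison of two independent groups". The distance measure, the taxonomic level of the profiles and any multiplicity rule are not stated.

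The paragraph on milk sampling, just before Aim 2, gives a purpose: to identify mouth bacteria that may have come from the mother's "breast milk or donor milk, a small sample of breast milk (3-5 mL) will be obtained" at the end of weeks 1 and 4, for 16S sequencing. Table 1 adds metagenomic sequencing for milk, under Covariates. The saliva row, under Oral Conditions, lists only the amount and type of bacteria.

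**The concern.** Two processing choices are written down, and each works against an aim of the protocol.

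- **Singletons.** A feature made of a single read occurs in one sample of one infant, so it cannot differ between groups in any detectable way. Open-reference picking lets reads that miss the reference form new OTUs, so the reference does not screen out error reads. Singletons tend to increase with read depth, so any richness or presence/absence measure would partly follow depth.
- **The 97% threshold.** Distinct but similar organisms in mouth and milk can fall into one OTU and appear shared. Telling milks apart matters here. Group 3 receives mother's or donor milk, and step 6 of the oral care procedure allows mother's milk in the cheek for eligible infants in all groups.

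At stake are some power in feature-level testing, the meaning of any richness summary, and the specificity of the comparison between mouth and milk.

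**Working it through.** The protocol gives no read depth, error rate, OTU count or alpha for this analysis, so it has no figure of its own to reproduce.

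**Inputs from the protocol:** 217 infants in 3 groups; weekly saliva for 4 weeks, so at most 217 × 4 = 868 samples; 97% similarity; V4 only; all singletons kept.

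**Assumptions:** equal allocation (217/3 ≈ 72 per group); two-sided alpha 0.05; a V4 amplicon of about 250 bases, range 150 to 300.

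**1. What a rare feature can show.** Two-sided Fisher exact test, 72 v 72, for a feature found in k infants, all in one group (the most favourable case):

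| k | p |
|---|---|
| 1 | 1.0 |
| 2 | 0.497 |
| 3 | 0.245 |
| 4 | 0.120 |
| 5 | 0.058 |
| 6 | 0.028 |

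At least 6 carriers, all in one group, are needed for p < 0.05. Dropping singletons loses no feature-level information on group differences.

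**2. Effect of a longer list.** Smallest k with p ≤ 0.05/m (Bonferroni, for illustration):

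| Features tested, m | Threshold | k needed |
|---|---|---|
| 200 | 0.00025 | 13 |
| 1,000 | 0.00005 | 15 |
| 5,000 | 0.00001 | 17 |
| 20,000 | 0.0000025 | 18 |

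A hundredfold longer list costs 5 more carriers. The loss is real but moderate, and it arises only if OTUs are tested with a correction.

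**3. Effect on ANOSIM.** Illustrative simulation: 3 × 30 samples, 100 real taxa, 3,000 reads per sample, 40 replicates, 199 permutations, 0 to 100 singletons added per sample.

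- Bray-Curtis on proportions: R = 0.031 and rejection rate 0.50 throughout.
- Presence/absence Jaccard: R fell from 0.025 with no singletons to 0.013 with 100 per sample. The rejection rate stayed between 0.45 and 0.53.

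**4. How many singletons.** This cannot be derived from the protocol. At an assumed 1 to 50 per sample, 868 samples would hold 868 to 43,400. Clustering itself limits base errors. With 7 mismatches tolerated in 250, a read needs 8 or more errors to leave its OTU. For 20,000 reads (assumed) and independent base errors, 20,000 × P(Binomial(250, e) ≥ 8) gives:

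- e = 0.1%: about 0.000005 per sample
- e = 0.5%: about 0.9
- e = 1%: about 81

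The number therefore depends almost entirely on an unknown residual error rate, and chimeras would add to it.

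**5. Resolution at 97%.** Allowed mismatches = 0.03 × length, rounded down:

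- 150 bases: 4.5, so 4
- 250 bases: 7.5, so 7
- 300 bases: 9.0, so 9

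**The case against.** The case for leaving the plan alone is substantial in several respects.

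- **The named tests are robust.** No richness or alpha-diversity outcome is specified, and abundance-weighted ANOSIM does not move. This stands.
- **The burden on STAMP is conditional.** If the profiles are taxon-level, most singletons merge into taxa. Without a multiplicity correction, a feature with p = 1 does not affect the others. This stands.
- **Laboratory steps limit error.** High-fidelity polymerase, pooled triplicate PCR and merged 300-base paired reads are specified, and a singleton that matches the reference is not plainly an error. This stands, and it weakens any claim about numbers.
- **A filter may come later.** The instruction describes OTU picking, and an analysis plan that is not shown could filter afterwards. That is possible, but the protocol specifies retention and goes on to testing with nothing in between, so such a filter would have to be reconciled with it.
- **Milk data go beyond 16S.** Table 1 lists metagenomics for milk but has no matching saliva entry, so it does not by itself provide tracing between the two.
- **Exact variants do not settle origin.** Two milks with identical V4 sequences would still look alike, and the protocol speaks only of possible origin. This stands, and it limits what the remedy can claim.

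A reader might infer that the data will be swamped by tens of thousands of false features, or that unrelated bacteria will be merged. The documents support neither. Read depth and error rate are not given, and sequences at least 97% identical in the same region are similar, not unrelated.

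**Conclusion.** The point holds in a limited form. The protocol fixes 97% open-reference OTUs with all singletons kept and states no later filter. Singletons cannot contribute to the between-group comparison. Their possible harm is confined to corrected OTU-level testing in STAMP and to any richness or presence/absence measure, and its size cannot be computed from the documents. It would be wrong to conclude that the community-level comparison is invalid, because abundance-weighted ANOSIM is practically unchanged.

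The threshold is the more direct problem. A tolerance of about 7 positions in 250 (4 to 9 over the assumed range of lengths) blurs the link between mouth and milk that the milk samples are meant to examine. The threshold is not the only limit, since a single short region restricts attribution even with exact variants.

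The group-size figures assume equal allocation and the p-value thresholds a two-sided alpha of 0.05. The plan should be changed because a better method exists for the same reads at low cost.

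**What to change.** Replace the 97% OTU step with denoising to exact sequence variants, including chimera removal. Process the reads from all 217 dyads in one run, including the 69 enrolled earlier, so that the two sets are handled alike. If OTUs are kept, drop singletons and apply a prevalence filter, chosen blind to group, before feature-level tests. A possible cut-off is presence in at least 5% of infants, which is 0.05 × 217 ≈ 11 infants.

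For milk origin, compare how often an infant shares variants with its own milk against how often it shares them with other mothers' milk, using permuted pairs. Multiples share a mother and must not be paired as unrelated. Report the result as shared-variant overlap, not as proof of source.

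The cost is bioinformatics time only, with no new samples and no effect on infants. Very rare taxa are lost, as are richness estimators that rely on singleton counts.
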